## **6.2. STATISTICS**

### **6.2.1. Description of planned statistical methods**

This study should allow us to evaluate the functioning of the application in a follow-up context in patients with lymphoma at high risk of relapse.

The patient sample for this analysis will consist of all patients, included in the study and meeting all the eligibility criteria described in Chapter 4, who have signed a consent.

The initial characteristics of the analysis population (demographic data, disease, previous and concomitant treatments, prognostic factors, etc.) and all the evaluation criteria described in paragraph 2 will be presented globally

For the qualitative variables, we will present the number as well as the percentage. For quantitative variables, we will present the median or the mean plus or minus the standard deviation depending on the normality of the variable, the minimums and maximums will also be indicated.

Events, as defined in chapter 2.1.2. (apart from relapse) will be described in terms of frequency by etiological type (HLT or HLG T according to the MedDRA classification) and by severity according to NCI CTCAE v4.02.

For the analysis of the censored data (overall survival and other timeframes of events), the survival curves will be plotted according to the Kaplan-Meier estimates, the medians of survival will be presented as well as their 95% confidence intervals.

For performing multivariate survival analyzes, the semi-parametric Cox model will be used to calculate the odds ratios which will be presented with their 95% confidence interval.

The sensitivity of the application to detect a relapse and / or significant complications will be calculated.

Quality of life scores will be calculated according to EORTC guidelines for the QLQ-C30. The quality of life will be described at each measurement time and compared to inclusion and then studied longitudinally using mixed analysis of variance models for repeated measures.

PHQ9 scores will be calculated according to the recommendations, described at each measurement time and compared to inclusion. The classes proposed in the literature ( $\leq 4$ ; 5-14;  $> 14$ ) will be used to describe the state of depression of patients.

The analyzes will be carried out with SAS 9.3 software (SAS Institute Inc. Cary, NC, USA).

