## **5.6. RULES FOR SUBJECT WITHDRAWAL**

### **5.6.1. Criteria for a study subject's early withdrawal**

Patients can withdraw their consent and request to withdraw from the trial at any time and for any reason, without losing the right to be treated by their doctor. The investigator may also prematurely discontinue a patient's participation in the trial for any reason that would serve the best interests of the patient, including the case of an intercurrent disease or an adverse event. In the event of premature discharge, at any time and for any reason, the investigator should notify the patient, if necessary, and document the reasons as fully as possible.

Test exits must be reported in particular for the following possible reasons:

- Death,
- Withdrawal of consent with the patient's request not to use the data already collected,
- Wrongly included,
- Choice of investigator,
- Patient choice,
- No seizure in the application for 6 consecutive weeks apart from a pathology or relapse preventing seizure,
- Lost view.

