### **6.2.1. Sample size determination**

The main objective of the study is to show that follow-up via the SENTINEL Lymphoma web-application could make it possible to better identify the significant complications occurring between two systematic follow-up consultations with the specialist in patients followed for high-risk lymphoma. relapse than with standard follow-up. The evaluation of the main objective will be carried out over 6 months of follow-up.

This study is based on a pooled triangle test analysis (24, 25, 26). Two groups will be composed, one will be monitored via the web-application, the other will be monitored in a standard way (consultation and imaging).

A 1: 1 randomization will assign the treatment group to the patient. Stratification on center, autologous transplant, PS, relapse and lymphoma type will be performed to ensure the comparability of our two populations at inclusion.

This sequential method will make it possible to evaluate during recruitment the diagnostic efficiency of significant complications outside systematic consultations while controlling the power (risk of accepting our null hypothesis wrongly) and the type I error (risk of rejecting our wrongly null hypothesis). This design allows us to consider stopping the trial as soon as the information gathered is sufficient to conclude. We will be able to conclude that the web-application is diagnostic efficiently or, on the contrary, that it is lacking in interest.

We set the risk of the first species alpha at 5%, the potency at 90%, we envisage that monitoring via the web-application allows us to identify significant complications between two systematic follow-ups in 90% of patients (i.e. 10% of patient presenting an event not identified early) against 60% (i.e. 40% of patient presenting an event not identified early) in the group followed in a standard way (i.e. a difference of 30%).

The early unidentified event is defined:

- in the web application follow up group by the absence of an alert in the following cases:
  - emergency hospitalization,
  - a medical consultation without follow-up with medical prescription (imaging / drug prescription)
  - a significant event at the classic follow-up consultation (very degraded PS, antibiotic therapy, supportive care with consultation, pulmonary embolism, sepsis, severe depression, etc.)
  
- – in the standard group in the following cases:

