  - emergency hospitalization, without medical consultation justifying this hospitalization,
  - a significant event at the classic follow-up consultation (very degraded PS, antibiotic therapy, supportive care with consultation, pulmonary embolism, sepsis, severe depression, etc.).

The events diagnosed during the follow-up consultation will be reviewed, in the form of a list (pooled data from the web-application follow-up and standard groups), by the coordinator, who will rule on the significance of the event.

- The hypotheses are written:

H0: The proportion of patients without an undiagnosed event outside the systematic consultation (follow-up visit and systematic imaging) is not different between the two groups.

H1: The proportion of patients without an undiagnosed event excluding systematic consultation (follow-up visit and systematic imaging) is higher with the web-application (by 30%) compared to standard follow-up (90% against 60%).

With 2 scheduled analyzes, it is necessary to include a maximum of 40 patients per group. The analyzes will be carried out every 2x20 patients included (20 in the control group and 20 in the group followed by web-application)

As the inclusions progress, two statistics will be calculated, one reflecting the efficiency and the other the amount of information accumulated. The whole will make it possible to draw a decisional graph, leaving the area thus drawn a conclusion will be possible. If we find ourselves above the zone we will conclude that H0 has been rejected, if we find ourselves below the zone we will conclude with an acceptance of H0 and therefore ineffective monitoring via the web-application.

CONFIDENTIAL

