### 6.2.3 Randomization

Randomization 1: 1 will be performed following minimization with stratification on the center, autologous transplant, PS, relapse and type of lymphoma. Randomization will be carried out by the investigator directly via the electronic CRF developed with ENNOV Clinical® software (Cenon, France).

Randomization will only be possible after the main data has been recorded on the e-CRF (date of signature of consent, stratification criteria, inclusion and non-inclusion criteria).

The patient's home group will be instantly displayed on the e-CRF after performing the randomization. A randomization confirmation email will also be sent to the investigator.

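### The only analysis set drops randomised patients later judged ineligible, with no all-randomised analysis and no rule that the judgement be blind to arm and outcome

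*Combined protocol and SAP*

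**What the plan says.** Section 6.2.1 (description of planned statistical methods) gives the sample for analysis as "all patients, included in the study and meeting all the eligibility criteria described in Chapter 4", with signed consent. It is the only analysis set in the document. The other section numbered 6.2.1 (sample size determination), which describes the triangular test, names no other, so this one governs the primary comparison by default.

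Four other places bear on how it would work:

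- **Section 6.2.3.** "Randomization will only be possible after the main data has been recorded on the e-CRF"; the data listed there include the inclusion and non-inclusion criteria. The allocated group is then shown to the investigator at once.
- **Section 5.6.1.** The reasons for leaving the trial include "Wrongly included", and also six consecutive weeks without an entry in the application.
- **Section 8.2.** The monitor's site visits check compliance with the eligibility criteria again.
- **Section 4.2.** Non-inclusion criterion 5 covers mental or psychiatric conditions that may compromise compliance. Criterion 6 covers inability to follow the protocol for psychological, social, family or geographical reasons.

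**The concern.** Randomisation protects the comparison only while patients are analysed in the groups to which they were allocated. Here eligibility is declared before allocation, so a patient who drops out of the analysis set as ineligible does so on a judgement made or revised afterwards. By then the arm is known to the investigator, and the outcome may be known too. The document does not say who makes that judgement, when, or with what information.

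The risk is not symmetric between arms. Criteria 5 and 6 turn on whether a patient can comply, and the most visible evidence of non-compliance, not using the application, can arise only in the web arm. A web-arm failure is a qualifying event without an alert. A patient who does not enter symptoms cannot trigger an alert, so non-users are more likely to count as failures. Rereading such a patient as never having been able to follow the protocol would remove a likely failure from one arm only.

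At stake is the type I error of a primary test on at most 40 patients per group, where a few patients can decide the result.

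**Working it through.** **1. The plan's own sample size.** Inputs from section 6.2.1 (sample size determination): "We set the risk of the first species alpha at 5%, the potency at 90"%, success rates "in 90% of patients (i.e. 10% of patient presenting an event not identified early) against 60"%, 1:1 allocation, and "With 2 scheduled analyzes, it is necessary to include a maximum of 40 patients per group". Sidedness is not stated, so both versions are shown.

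Fixed-sample formula: n = [z_α √(2 p̄(1−p̄)) + z_β √(p₁(1−p₁) + p₂(1−p₂))]² / δ², with p̄ = 0.75, p₁ = 0.9, p₂ = 0.6, δ = 0.3.

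- Two-sided: (1.960 × 0.6124 + 1.2816 × 0.5745)² / 0.09 = 41.7, so 42 per arm.
- One-sided: (1.645 × 0.6124 + 1.2816 × 0.5745)² / 0.09 = 33.8, so 34 per arm (41 with continuity correction).

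Triangular test on the log odds ratio, θ = ln 6 = 1.792, two equal looks, one-sided 0.025:

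- θ′ = 2 × 1.960 × 1.792 / (1.960 + 1.2816) = 2.167; a = 2 ln(20) / θ′ = 2.765; c = θ′/4 = 0.542.
- Solving a − 0.583√I = 2cI gives I = 1.825, so V = 2I = 3.65.
- n per arm = 2V / (0.75 × 0.25) = 38.9. At one-sided 0.05 the same steps give 33.1.

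The stated 40 per group is therefore reproduced to within two patients and is not in dispute. No allowance for exclusions is stated.

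**2. Exclusions unrelated to arm and outcome.** These cost power only. The documents give no exclusion rate, so a range is assumed. Power is from the fixed-sample formula at 90% against 60%.

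| Excluded (assumed) | Patients per arm | Two-sided 5% | One-sided 5% |
|---|---|---|---|
| 0% | 40 | 88.8% | 93.9% |
| 5% | 38 | 87.1% | 92.9% |
| 10% | 36 | 85.2% | 91.6% |
| 20% | 32 | 80.6% | 88.5% |

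**3. Exclusions related to arm and outcome.** The documents give nothing from which to estimate these, so this is an assumed worst case: no true difference, 40 randomised per arm, and k failures removed from the web arm only.

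With a common success rate of 75%, 30 successes are expected per arm. The web proportion becomes 30/(40 − k): 76.9% for k = 1, 78.9% for k = 2 and 81.1% for k = 3. The spurious differences are 1.9, 3.9 and 6.1 percentage points.

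For the type I error, let X and Y be independent Binomial(40, p) success counts and n₁ = 40 − k (or X, if there are fewer than k failures). The test is a single final pooled z-test, Z = (X/n₁ − Y/40) / √[p̂(1−p̂)(1/n₁ + 1/40)], where p̂ = (X+Y)/(n₁+40). Summing the exact probabilities over the rejection region gives:

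| k removed | p = 75%, one-sided 5% | p = 60%, one-sided 5% | p = 75%, one-sided 2.5% |
|---|---|---|---|
| 0 | 5.2% | 4.7% | 2.5% |
| 1 | 8.0% | 7.0% | 4.2% |
| 2 | 12.9% | 9.7% | 7.0% |
| 3 | 18.4% | 12.1% | 12.1% |

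In this scenario two removals at least double the error in every column. The calculation uses one final test because the plan prints no numerical boundaries for its two looks.

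**The case against.** The best defence is section 6.2.3. The e-CRF blocks randomisation until the consent date, stratification factors and eligibility criteria are recorded. The analysis-set wording (included, eligible, consented) mirrors that gate and may be meant only to describe patients properly entered, which would be nearly everyone randomised. No procedure for removing randomised patients from the analysis is described. This stands as a reason to expect few exclusions. It does not change what the sentence says: a patient found not to meet a criterion is outside the set, and section 8.2 provides the check that would find such a patient.

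Several stronger readings are tempting and are not supported:

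- **That exclusions will be made by people who know the arm and outcome.** The investigator sees the arm, but the document does not say who decides. Blinding of this judgement is unstated; unblinded exclusion is not shown.
- **That the wrongly-included exit removes a patient's data.** Section 5.6.1 lists it as a reason for leaving the trial. The only listed reason that mentions data not being used is withdrawal of consent with a request to that effect. The exit reason shows that ineligible inclusions are foreseen, no more.
- **That the baseline symptom score is open to reinterpretation.** It is a numerical cut-off recorded at baseline. Criteria 5 and 6 are the ones that rest on judgement.
- **That the harm can be read off power at different true rates.** Dropping two failures turns 34/40 (85%) into 34/38 (89.5%), close to the planned 90%. One might then compare the chance of rejection at true web rates of 85% and 90%. Exclusion alters the observed proportion and leaves the true rate where it was. Against 24/40 controls the fixed-sample z moves from 2.50 to 2.98, so the decision is the same. Against 27/40 it moves from 1.84 to 2.35, which crosses 1.96. Whether exclusions matter depends on how close the result is.

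Exclusion of ineligible patients can also be defended when it rests only on facts before randomisation, is judged blind to arm and outcome, and is applied with equal scrutiny to both arms. The plan states none of these conditions.

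**Conclusion.** The point holds as a defect in the definition of the analysis set. Followed as written, the plan removes randomised patients from its primary comparison after allocation, offers no all-randomised analysis beside it, and sets no safeguard on how ineligibility is judged.

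The size of any bias is unknown. The number of exclusions is probably small, and if they are unrelated to arm and outcome the loss is a few points of power. The rise in type I error from 5.2% to between 8.0% and 18.4% for one to three removals rests wholly on the assumptions that every removed patient is a web-arm failure and that a single final test is used. It shows how sensitive a 40-per-group comparison is and does not predict what will happen. The plan should be changed because the change is cheap and removes the risk; nothing in the document shows that biased exclusion is intended or likely.

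**What to change.** In section 6.2.1 (description of planned statistical methods):

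1. Define the primary analysis set as all randomised patients in their assigned arm, regardless of later eligibility review, application use or exit from the trial. Exclude only data that a patient has asked not to be used.
2. Keep the all-criteria-met set as a sensitivity analysis, with ineligibility judged on facts from before randomisation and blind to arm and outcome.
3. State how the 6-month primary endpoint is counted for patients who leave early. This needs saying because the exit for six weeks without an entry in the application can arise only in the web arm.

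The maximum stays at 40 per group, and no new assessments are needed. The cost is a sentence for the analysis set, a short rule for early exits, and slight dilution of the effect if a few ineligible patients remain in the primary analysis.

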### **1.5.2. Risks**

#### **1.5.2.1. Individual risks**

##### **Constraints**

The constraints are minimal and consist in competing:

- for all patients, a quality of life questionnaire and a questionnaire relating to depression at inclusion and then at follow-ups at 3, 6, 9 and 12 months
- for patients in the “web app follow up” arm, a satisfaction survey during the 6-month follow-up and at least every 14 days the specific questionnaire via a computer or a smartphone. The entry time is of the order of 1 to 2 minutes.

There is no further examination.

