## **2.2. SECONDARY OBJECTIVES AND ENDPOINTS**

### **2.2.1. Secondary objectives**

The interest of web-application monitoring will also be assessed in terms of:

- progression-free survival,
- overall patient survival at 2 years,
- estimated time between the diagnosis of a complication, allowed by the application, and the theoretical date of the scheduled subsequent follow-up,
- proportion of hospitalization for life-threatening emergencies,
- total number of complications observed,
- quality of life of patients,
- the degree of patient compliance with the use of the web application
- the degree of satisfaction with the use of the web-application and the implementation of web-monitoring,
- number of significant complications whatever they may be (but defined above), which have arisen and not identified via the application (sensitivity calculation),
- number of significant complications whatever they may be (but defined above), which have arisen and identified in the systematic follow-up group, excluding systematic follow-up,
- Performance Status at relapse,
- description of health consumption in the 2 groups.

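### PHQ-9, and QLQ-C30 as a first step, are compared with inclusion rather than between the randomised arms, and the terms of the QLQ-C30 and Cox models are not written

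*Combined protocol and SAP*

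**What the plan says.** Section 2.2.1 opens the list of secondary outcomes with "The interest of web-application monitoring will also be assessed in terms of". The list includes quality of life, progression-free survival (PFS), overall survival (OS), total complications and hospitalisation for life-threatening emergencies.

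The trial is randomised 1:1. The questionnaires are for both arms: section 1.5.2.1 lists "for all patients, a quality of life questionnaire and a questionnaire relating to depression at inclusion", with follow-up at 3, 6, 9 and 12 months, and the two schedules in section 5.3 agree.

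Section 6.2.1 (Description of planned statistical methods) then gives the analyses:

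- PHQ-9: "PHQ9 scores will be calculated according to the recommendations, described at each measurement time and compared to inclusion", followed by three depression classes. No model is named.
- QLQ-C30: described at each time, "compared to inclusion and then studied longitudinally using mixed analysis of variance models for repeated measures". No model terms are listed.
- Survival: Kaplan-Meier curves and medians with confidence intervals, not said to be drawn by arm. For multivariate analyses, "the semi-parametric Cox model will be used to calculate the odds ratios". No terms are listed.

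Other parts of the plan do name the groups. The primary hypotheses (section 6.2.1, Sample size determination) set one arm against the other, and section 2.2.1 asks for "description of health consumption in the 2 groups" and for complications "identified in the systematic follow-up group, excluding systematic follow-up".

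**The concern.** Whether the application helps is a question about the difference between arms. A comparison with inclusion answers another question: whether patients' scores move over time after lymphoma treatment. Scores could move for reasons common to everyone, such as recovery from treatment, with or without the application.

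Two misreadings follow. If the arms are pooled, a real common change may be credited to the application. If each arm is tested against its own baseline, a significant result in one arm and not in the other looks like a difference between arms, although no such difference was tested.

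Section 1.5.3 says the application could improve survival and quality of life. The analysis section does not say how that effect would be estimated. Where model terms, time point and scale are left open, they can also be chosen after the data are seen.

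**Working it through.** **1. Where an arm contrast is written.** In the planned-methods section the words arm, group and randomised do not occur. Comparison is mentioned twice, for QLQ-C30 and PHQ-9, both times with inclusion. No other section supplies a contrast for PHQ-9, QLQ-C30, OS or PFS. Outside the gap are:

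- the primary endpoint (hypotheses between arms);
- health consumption and the arm-specific complication counts (groups named in section 2.2.1);
- compliance, satisfaction and application sensitivity (application arm only).

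**2. The plan's own figure.** The 40 per group is for the primary endpoint only; no figure is given for a secondary outcome. It is plausible. For 90% against 60%, two-sided 5%, 90% power, the fixed-sample formula gives n = [1.96·√(2·0.75·0.25) + 1.2816·√(0.6·0.4 + 0.9·0.1)]² / 0.3² = (1.200 + 0.736)² / 0.09 ≈ 41.7, so 42 per arm. A simulated two-look triangular test at 20 and 40 per arm, one-sided 5%, had power 0.891.

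**3. Assumptions for the illustration.** The plan names no test for the comparison with inclusion, so I assume a paired t-test, two-sided 5%. The documents give no correlation between visits, so I use ρ = 0.3, 0.5 and 0.7. Changes d are in units of the single-visit SD. The SD of the change is √(2(1−ρ)), and power comes from the noncentral t with noncentrality d√n / √(2(1−ρ)).

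**4. Pooled comparison with inclusion, 80 patients, no application effect.**

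| Common change | ρ = 0.3 | ρ = 0.5 | ρ = 0.7 |
|---|---|---|---|
| 0.2 SD | 0.321 | 0.424 | 0.626 |
| 0.3 SD | 0.610 | 0.755 | 0.928 |
| 0.5 SD | 0.962 | 0.993 | 1.000 |

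These are correct detections of a change, but they carry no information about the application. In simulation the baseline-adjusted arm test stayed at 0.047 to 0.053.

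**5. Comparison within each arm, 40 per arm, no application effect.** With p the power in one arm, exactly one arm is significant with probability 2p(1−p). Example: d = 0.2, ρ = 0.5 gives noncentrality 0.2·√40 = 1.265, p = 0.235, and 2·0.235·0.765 = 0.360.

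| Common change | p (ρ = 0.3 / 0.5 / 0.7) | Exactly one arm significant |
|---|---|---|
| 0.2 SD | 0.181 / 0.235 / 0.357 | 0.296 / 0.360 / 0.459 |
| 0.3 SD | 0.346 / 0.457 / 0.666 | 0.453 / 0.496 / 0.445 |
| 0.5 SD | 0.741 / 0.869 / 0.978 | 0.384 / 0.228 / 0.043 |

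**6. What a baseline-adjusted arm contrast could detect.** The difference detectable with 80% power is close to (1.96 + 0.84)·√(2(1−ρ²)/n). For ρ = 0.5 and n = 40 this is 2.80·√(1.5/40) = 0.54. With the noncentral t, for ρ = 0.3 / 0.5 / 0.7:

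- 40 per arm: 0.605 / 0.549 / 0.453 SD
- 32 per arm (20% missing): 0.679 / 0.616 / 0.508 SD
- 20 per arm: 0.868 / 0.788 / 0.650 SD

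**7. Precision for OS.** With D deaths split evenly, the 95% CI is the hazard ratio divided and multiplied by exp(1.96·2/√D). The documents give no death rate for this population. For an assumed D of 10, 20, 30 or 40 the factor is 3.45, 2.40, 2.05 or 1.86.

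**The case against.** **An arm term is surely intended.** In a 1:1 randomised trial, arm is the natural term in a mixed model and in a Cox model. This stands for QLQ-C30, OS and PFS: the fault there is unstated terms, not a wrong analysis. It does not help PHQ-9, which has a stated comparison and no model that could hold an arm term.

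**The text may be incomplete.** A reader might take "all the evaluation criteria described in paragraph 2 will be presented globally" to mean that results will be pooled over arms. The sentence has no full stop and may be cut off, perhaps before a reference to the groups. I give it no weight; the point rests on the PHQ-9 and QLQ-C30 sentences.

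**The calculations show no error the plan must make.** This is fair. The test and the correlations are assumed, and the plan does not say that change will be tested within each arm. Equal and opposite changes in the two arms would cancel when pooled, but that holds by construction, so I do not count it. The figures only show how readily a change from inclusion can be misread.

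**The odds ratio is a wording slip, perhaps from translation.** Agreed. It should be corrected but adds nothing to the case.

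**These are secondary outcomes in a small trial.** This limits the severity. Low precision is a reason to report the arm difference with its interval; it does not make a change from inclusion answer the question.

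**Conclusion.** The point holds. For PHQ-9, following the plan as written leaves the question in section 2.2.1 unanswered. For QLQ-C30 the first stated step has the same defect, and the later model may or may not repair it. For survival the model terms need to be written down.

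If change were tested within arms, a spurious contrast (exactly one arm significant) would arise in about 30-46% of trials at a common change of 0.2 SD and 44-50% at 0.3 SD. This assumes 40 per arm, a paired t-test, ρ of 0.3 to 0.7 and no application effect.

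Three stronger readings are not supported. The plan does not exclude an arm comparison for all secondary outcomes: some are named by group, and two models could contain arm. The primary conclusion is not affected, since its contrast is explicit. Nor can the effect of earlier detection on PFS be sized from these documents: the only lead time given, 5 weeks in section 1.3, comes from a lung-cancer application. That caveat stays qualitative.

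This is a change that should be made, at modest severity.

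**What to change.** - **PHQ-9 and QLQ-C30.** As the analysis of the application effect, replace the comparison with inclusion by a mixed model for the M3 to M12 scores with baseline score, arm, visit and arm-by-visit. Report the arm difference with its 95% CI at one time point and, for QLQ-C30, on one scale, both named before analysis. Keep change from inclusion as description.
- **Analysis set.** Keep patients in their assigned arm. One exit reason in section 5.6.1 (six weeks without an application entry) can arise only in the application arm.
- **Survival.** Draw Kaplan-Meier curves by arm for OS and PFS, list the Cox terms with arm among them, and call the result a hazard ratio. State that PFS detection differs by arm (sections 5.2 and 5.3): six-monthly imaging in the standard arm, imaging prompted by an alert or clinical signs in the other. Earlier detection could therefore shorten PFS in the application arm.
- **Other two-arm secondary outcomes.** Report by arm, including life-threatening emergency hospitalisation (section 2.2.1) and time from diagnosis to start of care (section 2.2.2).
- **Status.** Label all of these results supportive and state their limited precision.

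The cost is SAP wording and SAS code; no new data are needed. The drawback is imprecision: at 40 per arm only differences of about 0.45-0.61 SD are detectable with 80% power.
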